### **11.3 Site monitoring**

Before study initiation, at a site initiation visit or at an investigator's meeting, a Novartis representative will review the protocol and data capture requirements (i.e. eCRFs) with the investigators and their staff. During the study, Novartis employs several methods of ensuring protocol and Good Clinical Practice (GCP) compliance and the quality/integrity of the sites' data. The field monitor will visit the site to check the completeness of participant records, the accuracy of data capture / data entry, the adherence to the protocol and to Good Clinical Practice, the progress of enrollment, and to ensure that study treatment is being stored, dispensed, and accounted for according to specifications. Key study personnel must be available to assist the field monitor during these visits. Continuous remote monitoring of each site's data may be performed by a centralized Novartis/CRA organization. Additionally, a central analytics organization may analyze data & identify risks & trends for site operational parameters, and provide reports to Novartis clinical teams to assist with trial oversight.

The investigator must maintain source documents for each participant in the study, consisting of case and visit notes (hospital or clinic medical records) containing demographic and medical information, laboratory data, electrocardiograms, and the results of any other tests or assessments. All information on eCRFs must be traceable to these source documents in the participant's file. The investigator must also keep the original ICF signed by the participant (a signed copy is given to the participant).

The investigator must give the monitor access to all relevant source documents to confirm their consistency with the data capture and/or data entry. Novartis monitoring standards require full verification for the presence of informed consent, adherence to the inclusion/exclusion criteria, documentation of SAEs, and of data that will be used for all primary variables. Additional checks of the consistency of the source data with the eCRFs are performed according to the study-specific monitoring plan. No information in source documents about the identity of the participants will be disclosed.

## **12 Data analysis and statistical methods**

Any data analysis carried out independently by the investigator should be submitted to Novartis before publication or presentation.

### **12.1 Analysis sets**

For all analysis sets, participants will be analyzed according to the study treatment received.

The safety analysis set will include all participants who received any study drug.

The PK analysis set will include all participants with at least one available valid (i.e. not flagged for exclusion) PK concentration measurement, who received any study drug.

The PD analysis set will include all participants who received any study drug and had no protocol deviations with relevant impact on PD data.

### **12.2 Participant demographics and other baseline characteristics**

Demographic and other baseline data including disease characteristics will be listed and summarized descriptively by treatment group for the Safety set.

Categorical data will be presented as frequencies and percentages. For continuous data, mean, standard deviation, median, minimum, and maximum will be presented.

Relevant medical histories and current medical conditions at baseline will be summarized by system organ class and preferred term by treatment group.

### **12.3 Treatments**

The Safety set will be used for the analyses below. Categorical data will be summarized as frequencies and percentages. For continuous data, mean, standard deviation, median, minimum, and maximum will be presented.

The duration of exposure to study treatment will be summarized by treatment group. Concomitant medications and significant non-drug therapies prior to and after the start of the study treatment will be listed and summarized according to the Anatomical Therapeutic Chemical (ATC) classification system, by treatment group. Additionally, rescue therapy as well as concomitant anti-histamines will be summarized by treatment group.

## **12.4 Analysis of the primary endpoint(s)/estimand(s)**

The primary aim of the study is to assess efficacy of CMK389 in participants with moderate to severe AD. This will be evaluated by assessing the IGA response at Week 16. This analysis will be performed on the PD analysis set. For the efficacy analyses, the two placebo groups (placebo s.c. and i.v.) will be pooled together.

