## 1 Introduction

### 1.1 Scope of document

The Reporting and Analysis Plan (RAP) documents contain detailed information to aid the production of Statistics & Programming input into the Clinical Study Report (CSR) for trial “**CCMK389B12201**”.

The Statistical Analysis Plan (SAP) describes the implementation of the statistical analysis planned in the protocol.

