### 1.2 Study reference documentation

Study Protocol v02 is available at the time of finalization of SAP.

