## 4 Statistical methods: Analysis sets

For all analysis sets, participants will be analyzed according to the study treatment received. For participants for which the actual treatment received does not match the randomized treatment, the treatment actually received will be used for the analysis.

The safety analysis set will include all participants who received any study drug.

Comercially Confidential Information

The PD analysis set will include all participants who received any study drug and had no protocol deviations with relevant impact on PD data.

The analysis sets and protocol deviation codes are related as follows:

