**Table 4-1 Subject classification rules**

Analysis set	PD codes that cause a subject to be excluded	Non-PD criteria that cause a subject to be excluded
Safety set	None	No treatment taken
PD analysis set	None	No treatment taken, no valid PD data

If updates to this table are needed, an amendment to the SAP needs to be implemented prior to DBL.

Comercially Confidential Information

Commercially Confidential Information

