## **6 Statistical methods for Pharmacodynamic (PD) parameters**

### **6.1 Primary objective**

The primary objective of this study is to assess efficacy of CMK389 in participants with moderate to severe AD. This analysis will be performed on the safety analysis set.

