#### **6.1.1 Variables**

The primary variable is the IGA response at Week 16, defined as clear or almost clear at Week 16 with at least 2-point reduction from baseline.

The IGA rating scale is a Validated Investigator Global Assessment scale for Atopic Dermatitis (vIGA-ADTM) and it describes the overall disease severity for the whole body on a 5-point scale: clear (0), almost clear (1), mild (2), moderate (3), and severe (4).

For the descriptive analysis ([Section 6.1.2](#)) the placebo groups (i.e. placebo i.v. and placebo s.c.) will be presented both separately and pooled. For the inferential analysis ([Section 6.1.3](#)), the two placebo groups (placebo s.c. and i.v.) will be only presented pooled.

Baseline is considered to be the last assessment (including those from unscheduled visits) obtained before the first dose of study treatment.

The primary clinical question of interest is: What is the effect of CMK389 versus placebo on IGA response after 16 weeks of treatment in patients with moderate or severe atopic dermatitis without any relevant use of prohibited medication or use of rescue medication taken after first 6 weeks.

Prohibited or rescue medication are relevant when their use may have a potential confounding effect on the efficacy assessment.

This estimand will enable assessment of the effect of CMK389 for the full duration in the absence of relevant use of prohibited medication or use of rescue medication taken after the first 6 weeks.

The primary estimand is described by the following attributes:

**Population:** Adult participants with moderate to severe atopic dermatitis is the target population for biologics (Beck et al 2014, Simpson et al 2016) and is defined by an IGA score of moderate to severe (3 or 4) and an EASI score of at least 12 as defined by the study inclusion and exclusion criteria who were randomized to treatment. Further details about the population are provided in Section 5 of the protocol. This implies that analyses will be based on the safety analysis set.

**Endpoint:** IGA response at week 16, where IGA response is defined as clear or almost clear and with at least a 2-point reduction compared to baseline and no use of confounding therapy before the assessment time point.

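### Does it matter that the protocol puts the primary Week 16 IGA analysis on the PD set while the SAP puts it on the safety set?

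*Protocol*

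**What the plan says.** Protocol 12.4 assigns the Week 16 IGA response to the PD set: "This analysis will be performed on the PD analysis set". Protocol 12.1 defines that set: "The PD analysis set will include all participants who received any study drug and had no protocol deviations with relevant impact on PD data". The safety set in the same section is everyone who received study drug.

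SAP 6.1 assigns the same analysis differently: "This analysis will be performed on the safety analysis set". SAP 6.1.1 repeats this under the population attribute of the estimand: "This implies that analyses will be based on the safety analysis set".

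SAP section 4 keeps the protocol's wording for the PD set, including that its members "had no protocol deviations with relevant impact on PD data". Table 4-1, which turns the definitions into rules, lists no excluding deviation codes for the PD set. Its only exclusion criteria for that set are "No treatment taken, no valid PD data".

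On its own status, SAP 1.1 says that it "describes the implementation of the statistical analysis planned in the protocol", and SAP 1.2 says "Study Protocol v02 is available at the time of finalization of SAP".

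**The concern.** Two documents name two denominators for the primary response rate. A SAP that presents itself as implementing the protocol would be expected either to agree with it or to say where it departs, and the visible SAP text does not mention that Protocol 12.4 chose another set.

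The difference could also touch the estimand. Under the composite strategy, participants who use relevant prohibited medication, take rescue medication after Week 6, or stop treatment for inefficacy or an AD-related adverse event must stay in the analysis as non-responders. Use of prohibited medication is also a natural candidate for a deviation affecting PD data. If the protocol's filter were applied literally, some participants whom the estimand counts as failures might be dropped, and the response rate in their arm would rise.

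**Working it through.** This is mainly a comparison of texts. The plan's one power-type figure (80% in Protocol 12.8.1) does not help: it cannot be reproduced with the dual criteria and the placebo prior redacted, and the question does not depend on it.

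**1. The rules side by side**

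| | Safety set | PD set |
|---|---|---|
| Protocol 12.1 | all dosed | all dosed, minus deviations relevant to PD data |
| SAP section 4 text | all dosed | same as protocol |
| SAP Table 4-1, deviation codes | none | none |
| SAP Table 4-1, other exclusions | not dosed | not dosed, or no valid PD data |
| Used for primary analysis by | SAP 6.1, 6.1.1 | Protocol 12.4 |

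Both documents analyse participants by treatment received in every set, so that does not separate the two.

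**2. Who differs under the SAP's rules.** With no excluding deviation code, the only people in the safety set but not in the PD set are dosed participants without valid PD data. There are two cases.

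- *No composite event.* SAP 6.1.3.2 plans no imputation for the primary endpoint. A participant with no usable IGA therefore contributes no Week 16 response, whichever set is named. This assumes that the rate is computed among participants with a determined response.
- *Composite event*, for example stopping for inefficacy with no usable later IGA. SAP 6.1.1 and 6.1.3.1 classify this person as a non-responder. The safety set keeps them; the PD set might not. Here the SAP's choice is the one that matches the estimand.

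**3. Whether the protocol really drops composite-event participants.** No passage codes use of prohibited medication as an excluding deviation. Protocol 9.1.1.1 says that a participant who stops because of prohibited medication is not replaced and counts as a non-responder in the primary analysis. Protocol 12.4.3 says the same of composite events generally. Read as a whole, the protocol keeps these participants in, as the SAP does.

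**4. Whether the SAP states and justifies its set.** It states it in 6.1 and again in 6.1.1, where it presents the set as a consequence of the estimand population. What is not visible is only a sentence linking this to Protocol 12.4.

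**The case for a change.** The strongest opposing case is that the two assignments cannot both be followed, that the sets are not synonyms, and that the SAP treats set membership as controlled content: a change to Table 4-1 needs a SAP amendment before database lock. A change in which set carries the primary analysis would seem to deserve at least a line. It can be added that the section 4 wording and Table 4-1 describe the PD set differently.

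In a trial this small, each participant counts. Take the design rates in Protocol 12.8.1 (7% on placebo and a 36-point difference, so 43% on active) with 32 and 16 participants and no prior. Expected responders are 0.43 × 32 = 13.76 and 0.07 × 16 = 1.12.

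- None removed: 13.76/32 − 1.12/16 = 36.0 points.
- One active non-responder removed: 13.76/31 − 1.12/16 = 44.39 − 7.00 = 37.4.
- One placebo non-responder removed: 13.76/32 − 1.12/15 = 43.00 − 7.47 = 35.5.
- One of each removed: 44.39 − 7.47 = 36.9.
- One active *responder* removed: 12.76/31 − 1.12/16 = 41.16 − 7.00 = 34.2.

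The textual mismatch stands. The arithmetic is correct but does not measure its effect. The counts are assumed, the sign depends on who is removed, the placebo prior that the plan uses is left out, and the filter that would remove anyone has no code behind it in Table 4-1. The section 4 wording can be read as a general rule whose qualifying codes the table then lists, and there are none. The absence of a recorded change cannot be tested either: SAP sections 2, 3 and 5, the model text in 6.1.3 and the appendix are redacted, and the front matter was removed.

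**Conclusion.** The labels conflict, but no change to the plan is needed. The SAP is the document from which the analysis is programmed. It names the safety set unambiguously, ties it to the estimand, and retains composite-event participants as non-responders. That is the analysis one would ask for if the question were open. Aligning Protocol 12.4 with it, or adding a cross-reference in the SAP, would improve the paper trail but leave the primary result as it is. In a study that describes itself as non-confirmatory, that gain is too small to count as a correction.

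As to size, no participant is removed by a deviation code under Table 4-1, and no effect on the primary estimate is demonstrated. The remaining difference is limited to dosed participants without valid PD data, whose number is not given.

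This rests on three assumptions: that the analysis follows the SAP; that Table 4-1 stays as written up to database lock; and that the supplied protocol is the version the SAP cites, which cannot be confirmed because the title page was removed.

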### **12.4.1 Definition of primary endpoint(s)/estimand(s)**

The primary estimand, including the primary endpoint, is defined in [Section 2.1](#). It is based on the IGA response at week 16.

### **12.4.2 Statistical model, hypothesis, and method of analysis**

The IGA data will be listed and summarized by treatment group. Placebo groups will be pooled. Summary tables will be presented by treatment group and visit which include absolute and relative frequencies.

Commercially Confidential Information

Commercially Confidential Information

#### **12.4.3 Handling of remaining intercurrent events of primary estimand**

Use of any therapy (prohibited or rescue medication taken after the first 6 weeks) as well as any study treatment discontinuation due to lack of efficacy or due to an AE related to AD are considered as unfavorable outcomes, and therefore the participants will be treated as non-responders (composite strategy). Study treatment discontinuation due to other reasons and AEs not related to AD or due to lack of tolerability will be handled with a treatment policy strategy (i.e. they will be ignored).

#### **12.4.4 Handling of missing values not related to intercurrent event**

Missing data imputations will be discussed in the Statistical Analysis Plan (SAP) in detail.

## 12.5 Analysis of secondary endpoints/estimands

Assessing safety and tolerability of CMK389 in participants with AD is the secondary CCI objective of the study.

### 12.5.1 Safety endpoints

For all safety analyses, the safety set will be used. All tables, figures and listings tables will be presented by treatment group and pooled placebo group (placebo s.c. and placebo i.v.).

Safety summaries (tables, figures) include only data from the on-treatment period with the exception of baseline data which will also be summarized where appropriate (e.g. change from baseline summaries). In addition, a separate summary for death including on treatment and post treatment deaths will be provided, if there were death during the study. In particular, summary tables for adverse events (AEs) will summarize only on-treatment events, with a start date during the on-treatment period (treatment-emergent AEs).

The on-treatment period lasts from the date of first administration of study treatment to 112 days after the date of the last actual administration of any study treatment.

### Adverse events

All information obtained on adverse events will be displayed by treatment group (CMK389 10 mg/kg i.v, Placebo i.v, CMK389 300 mg s.c, Placebo s.c, and Pooled placebo) and participant.

The number (and percentage) of participants with treatment emergent adverse events (events started after the first dose of study medication or events present prior to start of double-blind treatment but increased in severity based on preferred term) will be summarized in the following ways:

- by treatment, primary system organ class and preferred term.
- by treatment, primary system organ class, preferred term and maximum severity.

Separate summaries will be provided for study medication related adverse events, death, serious adverse events, and other significant adverse events leading to discontinuation.

The number (and proportion) of participants with adverse events of special interest (i.e. hypersensitivity reactions such as serum sickness and anaphylaxis) will be summarized.

A participant with multiple adverse events within a primary system organ class is only counted once towards the total of the primary system organ class.

Commercially Confidential Information

Commercially Confidential Information

Commercially Confidential Information

Commercially Confidential Information

## 12.8 Sample size calculation

### 12.8.1 Primary endpoint(s)

The study is powered for the comparison between CMK389 10mg/kg i.v. vs placebo where both groups of placebo i.v. and placebo s.c. will be pooled together. The additional treatment group of CMK389 300mg s.c. will not be statistically tested against placebo.

CCI illustrates the operating characteristics for the design with 32 participants randomized to CMK389 10mg/kg i.v. and 16 participants on placebo.

The MAP prior for the placebo group is included in the analysis. Assuming the true treatment difference in IGA rate is 36% between CMK389 10mg/kg i.v. and placebo and assuming that the true placebo IGA rate is 7%, the probability of meeting the dual efficacy criteria as stated in [Section 12.4.2](#) is 80%.

Commercially Confidential Information

### **12.8.2 Secondary endpoint(s)**

Not applicable.

## **13 Ethical considerations and administrative procedures**

### **13.1 Regulatory and ethical compliance**

This clinical study was designed and shall be implemented, executed and reported in accordance with the ICH Harmonized Tripartite Guidelines for Good Clinical Practice, with applicable local regulations (including European Directive 2001/20/EC, US CFR 21), and with the ethical principles laid down in the Declaration of Helsinki.

### **13.2 Responsibilities of the investigator and IRB/IEC**

Before initiating a trial, the investigator/institution must obtain approval/favorable opinion from the Institutional Review Board/Independent Ethics Committee (IRB/IEC) for the trial protocol, written ICF, consent form updates, participant recruitment procedures (e.g., advertisements) and any other written information to be provided to participants. Prior to study start, the investigator is required to sign a protocol signature page confirming his/her agreement to conduct the study in accordance with these documents and all of the instructions and procedures found in this protocol and to give access to all relevant data and records to Novartis monitors, auditors, Novartis Quality Assurance representatives, designated agents of Novartis, IRBs/IECs, and regulatory authorities as required. If an inspection of the clinical site is requested by a regulatory authority, the investigator must inform Novartis immediately that this request has been made.

### **13.3 Publication of study protocol and results**

The protocol will be registered in a publicly accessible database such as EudraCT. In addition, after study completion (defined as last patient last visit) and finalization of the study report the results of this trial will be submitted for publication and posted in a publicly accessible database of clinical trial results, such as the Novartis clinical trial results website and all required Health Authority websites (e.g. EudraCT etc.)

For details on the Novartis publication policy including authorship criteria, please refer to the Novartis publication policy training materials that were provided to you at the trial investigator meetings.

### **13.4 Quality Control and Quality Assurance**

Novartis maintains a robust Quality Management System (QMS) that includes all activities involved in quality assurance and quality control, to ensure compliance with written Standard Operating Procedures as well as applicable global/local GCP regulations and ICH Guidelines.

Audits of investigator sites, vendors, and Novartis systems are performed by auditors, independent from those involved in conducting, monitoring or performing quality control of the clinical trial. The clinical audit process uses a knowledge/risk based approach.

Audits are conducted to assess GCP compliance with global and local regulatory requirements, protocols and internal SOPs, and are performed according to written Novartis processes.

## **14 Protocol adherence**

This protocol defines the study objectives, the study procedures and the data to be collected on study participants. Additional assessments required to ensure safety of participants should be administered as deemed necessary on a case by case basis. Under no circumstances including incidental collection is an investigator allowed to collect additional data or conduct any additional procedures for any purpose involving any investigational drugs under the protocol, other than the purpose of the study. If despite this interdiction prohibition, data, information, observation would be incidentally collected, the investigator shall immediately disclose it to Novartis and not use it for any purpose other than the study, except for the appropriate monitoring on study participants.

Investigators ascertain they will apply due diligence to avoid protocol deviations. If an investigator feels a protocol deviation would improve the conduct of the study this must be considered a protocol amendment, and unless such an amendment is agreed upon by Novartis and approved by the IRB/IEC and Health Authorities, where required, it cannot be implemented.

